10.4. Appendix 4: Study Phases and Treatment Emergent Adverse Events

10.4.1. Study Phases

Assessments and events will be classified according to the time of occurrence relative to the start and/or stop of study treatment.

Study Phase	Definition
Pre-Treatment	Date (and time) \leq Study Treatment Start Date (and time)
On-Treatment	Study Treatment Start Date (and time) $<$ Date (and time) \leq Study Treatment Stop Date + 3 days
Post-Treatment	Date $>$ Study Treatment Stop Date + 3 days

10.4.1.1. Study Phases for Concomitant Medication

COPD medication combinations taken at screening will include all COPD medications that were taken on the day of the screening visit, excluding medications that stopped on the day of the screening visit.

Treatment phases for summaries of COPD and non-COPD concomitant medications will be classified as follows:

Study Phase	Definition
Prior to Treatment	Medications taken on or before the day before treatment start date defined as: (conmed start date $<$ treatment start date or 'Taken prior to study?' is 'Yes' or study treatment not started or conmed start date is missing) Note: Prior concomitant medication data will only be summarized for COPD medications. COPD concomitant medications that have been stopped greater than three calendar months prior to Visit 1 and non-COPD concomitant medications that have been stopped prior to randomization will not be included in any summary tables
On-treatment	If study treatment stop date $>$ study treatment start date, then this includes medications taken between the study treatment start date and study treatment stop date - 1 (inclusive) defined as follows: (conmed start date $<$ study treatment stop date or conmed start date is missing) and (conmed stop date \geq study treatment start date or (conmed stop date is completely missing and study treatment start date is non-missing)) If study treatment stop date = study treatment start date, then this includes medications taken on the study treatment start date (which is equal to the study treatment stop date) defined as follows. (conmed start date \leq study treatment stop date or conmed start date is missing) and (conmed stop date \geq study treatment start date or (conmed stop date is completely missing and study treatment start date is non-missing))
Post-treatment	If study treatment stop date $>$ study treatment start date, then this includes medications taken after the study treatment stop date defined as follows: (conmed stop date \geq study treatment stop date or (conmed stop date is completely missing and study treatment stop date is non-missing)) If study treatment stop date = study treatment start date, then this includes medications

Study Phase	Definition
	taken after the study treatment stop date + 1 defined as follows. (conmed stop date > study treatment stop date or (conmed stop date is completely missing and study treatment stop date is non-missing))

NOTES:

- A concomitant medication will be classed in every period of the study in which it was taken.
- See Section 10.7.2.1 for handling of partial dates.
- If the study treatment stop date is missing, it will be imputed as described in Section 10.6.1.

10.4.1.2. Study Phases for Event Data

Classification of an AE as having onset on-treatment will be made with reference to the study treatment start and stop dates and the event onset date. If the event onset date is missing, then the event will be considered on-treatment.

Study Phase	Definition
Pre-treatment	If onset date is prior to treatment start date Start Date < Study Treatment Start Date
On-treatment	If onset date is on or after treatment start date & on or before treatment stop date + 3 days. Study Treatment Start Date ≤ Start Date ≤ Study Treatment Stop Date + 3 days
Post-treatment	If onset date is after treatment stop date + 3 days. Start Date > Study Treatment Stop Date + 3 days

Note: assume on-treatment unless there is evidence to the contrary

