10.4.1.3. Treatment Emergent AEs

If the study treatment stop date is missing, it will be imputed as described in Section 10.6.1.

Flag	Definition
Treatment Emergent	If AE onset date is on or after treatment start date & on or before the treatment stop date + 3 days 
 • Study Treatment Start Date ≤ AE Start Date ≤ Study Treatment Stop Date + 3 days

NOTES:

- Time of study treatment dosing and start/stop time of AEs should be considered, if collected.

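### Appendix 4 gives two opposite phases to an adverse event dated on the treatment start date: pre-treatment under SAP 10.4.1, on-treatment under 10.4.1.2, with no order of precedence

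*SAP*

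**What the plan says.** Four places in the SAP bear on how an adverse event is placed relative to the start of treatment.

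- **10.4.1 (Study Phases).** The lead sentence reads "Assessments and events will be classified according to the time of occurrence relative to the start and/or stop of study treatment". In the table below it, a date (and time) equal to treatment start is pre-treatment. On-treatment requires a strictly later one: "Study Treatment Start Date (and time) $<$ Date (and time) \leq Study Treatment Stop Date + 3 days".
- **10.4.1.2 (Study Phases for Event Data).** Pre-treatment is "Start Date < Study Treatment Start Date", a strict inequality on dates. On-treatment is "If onset date is on or after treatment start date & on or before treatment stop date + 3 days", so equality with the start date counts as on-treatment. For undated events it says "If the event onset date is missing, then the event will be considered on-treatment". A note under the table tells the reader to presume on-treatment in the absence of contrary evidence.
- **10.4.1.3 (Treatment Emergent AEs).** The flag uses the same date window, "If AE onset date is on or after treatment start date & on or before the treatment stop date + 3 days", and adds "Time of study treatment dosing and start/stop time of AEs should be considered, if collected". It does not mention a missing onset date.
- **10.7.2.1 (partial dates).** If only the day of onset is missing and the first of the month precedes treatment, the onset is set to the treatment start date. The event is then declared on-treatment, with a reference to Appendix 4. Completely missing dates are not imputed.

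**The concern.** The table in 10.4.1 and the table in 10.4.1.2 both claim adverse events, and they treat the start date in opposite ways. A programmer who follows the general table puts an untimed first-day event before treatment. One who follows the event table puts it on treatment. The SAP does not say which prevails.

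Equality with the start date is also not only a matter of chance, because 10.7.2.1 produces it by rule for some partial dates.

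The phase decides whether a serious adverse event is counted in Table 3.6 (pre-treatment) or Table 3.7 (on-treatment), and whether an event of special interest enters Table 3.9 (on-treatment only). Section 2.1 gives the primary interest in safety results as a reason for reporting on the Safety population, so these are displays that readers will look at.

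**Working it through.** The plan states no figure to reproduce. The check is to apply each rule as written to a set of onsets. To fix ideas, assume treatment starts on 10 June 2018 at 09:00; the SAP gives no such dates.

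| Onset | 10.4.1 | 10.4.1.2 table (dates) | 10.4.1.3 flag |
|---|---|---|---|
| Day before start | pre | pre | no |
| Day 1, no time | **pre** | **on** | yes |
| Partial date, imputed to start date | **pre** | **on** | yes |
| Day 1, timed exactly at first dose | **pre** | **on** | yes |
| Day 1, timed before first dose | pre | on by the table; pre if the note admits clock time | no |
| Day 1, timed after first dose | on | on | yes |
| Day 2 | on | on | yes |
| Stop date + 3 days | on | on | yes |
| Stop date + 4 days | post | post | no |
| Onset date completely missing | cannot be determined | on | no rule given |

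**Start-date boundary.** For an untimed onset on 10 June, 10.4.1 asks whether 10 June ≤ 10 June. It is, so the event is pre-treatment. Section 10.4.1.2 asks whether 10 June < 10 June. It is not, so the event is on-treatment.

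**Partial date.** An onset recorded only as June 2018 would first become 1 June. That precedes 10 June, so 10.7.2.1 resets it to 10 June and calls it on-treatment. This agrees with 10.4.1.2 and contradicts 10.4.1, although both belong to the appendix that 10.7.2.1 cites.

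**Clock time.** An onset timed at 07:00 on 10 June precedes the first dose. Under 10.4.1.3, with times considered, it is not treatment-emergent. The 10.4.1.2 table compares dates only and makes it on-treatment, unless its note is read as letting the recorded time overturn that result. The SAP does not say whether it does.

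**Where the rules agree.** They agree for any onset before the start date, for a Day 1 onset timed after dosing, and for later onsets, including the end of the window.

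**Size.** One participant moved across the boundary changes an arm's percentage by 1/n. At the planned 50 per arm (section 2.3) this is 1/50 = 2 points. Section 2.4 says that few participants contributed data but gives no arm sizes. Purely as an assumed range, 25 per arm gives 1/25 = 4 points and 10 per arm gives 1/10 = 10 points. The number of affected events is unknown and may be zero.

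**The case against.** The strongest reply is that the structure of Appendix 4 already settles the matter. A general table is followed by one for concomitant medication and one for events, and the event table is complete in itself. Other sections fit that reading. Section 10.7.2.1 reaches its on-treatment result only through 10.4.1.2. Section 10.6.4 cites 10.4.1 for minimum, maximum and worst-case assessments. Section 5.2 presumes that an untimed Day 1 assessment precedes the first dose, which explains the boundary in 10.4.1. This is good evidence of intent, and it stands as such. It does not remove the conflict, because 10.4.1 names events expressly and nothing says that the later table overrides it.

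Three stronger readings are tempting and should be resisted:

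- **One event with three incompatible outcomes.** A reader might infer this for a Day 1 event timed before the first dose. The note in 10.4.1.2 can reasonably be read as making that event pre-treatment, which matches 10.4.1 and the absence of the flag. The case also needs event times, and the SAP says only that they count if collected.
- **A contradiction over missing onset dates.** Section 10.4.1.3 is silent on them; it does not state the opposite of 10.4.1.2. This is a gap in the flag.
- **On-treatment and treatment-emergent counts that cannot be reconciled.** No display title in Appendix 10 uses the treatment-emergent flag, so no listed pair of counts is shown to disagree.

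The reply is also right that the reach is narrow. Tables 3.6 and 3.7 cover serious events only, and Table 3.9 covers the infective pneumonia query only. Events are also listed individually (Listings 15, 18 and 19), so a boundary case can be inspected.

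**Conclusion.** The point holds as a drafting conflict of minor impact. As worded, 10.4.1 and 10.4.1.2 assign opposite phases to an adverse event dated on the treatment start date when no time is recorded or when the date was imputed there. The SAP's own handling of partial dates shows that the on-treatment result is intended, so it is 10.4.1 that is misstated for adverse events. A secondary inconsistency is that the instruction on clock times is attached to the flag and not to the phase table, where only a general note softens the date rule.

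The consequence is limited to whether a boundary serious event is counted in Table 3.6 or 3.7, and whether a boundary event of special interest enters Table 3.9. It arises only if such an event exists, and the SAP gives no count. One participant is worth 2 points at the planned 50 per arm; any larger figure rests on an assumed smaller arm. With no formal analysis planned (section 2.4), no inference depends on it.

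**What to change.** 1. In 10.4.1, limit the lead sentence and table to assessments, and state that 10.4.1.2 governs adverse events.
2. Use one rule for adverse-event phase and for the treatment-emergent flag. Where onset time and first-dose time are both recorded, an onset before the first dose is pre-treatment and not treatment-emergent; say that this is what the note in 10.4.1.2 means by contrary evidence. Where either time is missing, a Day 1 onset is on-treatment and treatment-emergent.
3. Carry the 10.4.1.2 convention for a missing onset date into 10.4.1.3, so that such an event is flagged treatment-emergent unless there is evidence otherwise.

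The cost is a few lines of SAP text and one shared derivation in the adverse-event dataset. No new data are needed. It is best settled before the randomization codes are released.

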10.4.1.3. Treatment Emergent AEs

If the study treatment stop date is missing, it will be imputed as described in Section 10.6.1.

Flag	Definition
Treatment Emergent	If AE onset date is on or after treatment start date & on or before the treatment stop date + 3 days 
 • Study Treatment Start Date ≤ AE Start Date ≤ Study Treatment Stop Date + 3 days

NOTES:

- Time of study treatment dosing and start/stop time of AEs should be considered, if collected.

10.5. Appendix 5: Data Display Standards & Handling Conventions

10.5.1. Reporting Process

Software	

 The currently supported versions of SAS software will be used. 	
Reporting Area	
HARP Server	: uk1salx00175
HARP Compound	: GSK1325756
Analysis Datasets	

 Analysis datasets will be created according to IDSL standards. 	
Generation of RTF Files	

 RTF files will be generated for the final reporting effort 	

10.5.2. Reporting Standards

General

 The current GSK Integrated Data Standards Library (IDSL) will be applied for reporting, unless otherwise stated (IDSL Standards Location: https://spope.gsk.com/sites/IDSLLibrary/SitePages/Home.aspx): 
 4.03 to 4.24: General Principles 5.01 to 5.08: Principles Related to Data Listings 6.01 to 6.11: Principles Related to Summary Tables 7.01 to 7.13: Principles Related to Graphics
Formats

 GSK IDSL Statistical Principles (4.24) for decimal places (DP's) will be adopted for reporting of data based on the raw data collected, unless otherwise stated. Numeric data will be reported at the precision collected on the eCRF or provided by the vendor. The reported precision from non eCRF sources will follow the IDSL statistical principles but may be adjusted to a clinically interpretable number of DP's. 
 SGRQ will have a min and max to 1 decimal places (dp) and then follow IDSL standards for reporting other summary statistics. CAT will have a min and max to 0 dp and then follow IDSL standards for reporting other summary statistics. Categories will be based on rounded values to the precision collected on the eCRF or vendor provided data Summary Statistics of continuous data will include number of participants, mean, SD, median, minimum and maximum.
Planned and Actual Time

 Reporting for tables, figures and formal statistical analyses: 
 Planned time relative to dosing will be used in figures, summaries, statistical analyses and calculation of any derived parameters, unless otherwise stated. The impact of any major deviation from the planned assessment times and/or scheduled visit days on the analyses and interpretation of the results will be assessed as appropriate. Reporting for Data Listings: 
 Planned and actual time relative to study drug dosing will be shown in listings (Refer to IDSL Statistical Principle 5.05.1).

 • Unscheduled or unplanned readings will be presented within the participant’s listings. 	
Unscheduled Visits	

 • Unscheduled visits will not be included in summary tables and/or figures except as part of a maximum/minimum/worst case post-baseline assessment • All unscheduled visits will be included in listings. 	
Descriptive Summary Statistics	
Continuous Data	Refer to IDSL Statistical Principle 6.06.1
Categorical Data	N, n, frequency, %
Graphical Displays	

 • Refer to IDSL Statistical Principals 7.01 to 7.13. 	

10.6. Appendix 6: Derived and Transformed Data

10.6.1. General

Multiple Measurements at One Analysis Time Point

 • Mean of the measurements will be calculated and used in any derivation of summary statistics but if listed, all data will be presented. • If there are two values within a time window (as per Section 10.3.1) the value closest to the target day for that window will be used. If values are the same distance from the target, then the mean will be taken. • Participants having both High and Low values for Normal Ranges at any post-baseline visit for safety parameters will be counted in both the High and Low categories of “Any visit post-baseline” row of related summary tables. This will also be applicable to relevant Potential Clinical Importance summary tables.
Study Day

 • Calculated as the number of days from First Dose Date: 
 • Ref Date = Missing → Study Day = Missing • Ref Date < First Dose Date → Study Day = Ref Date – First Dose Date • Ref Date ≥ First Dose Date → Study Day = Ref Date – (First Dose Date) + 1
Study Treatment Stop Date

 • If the study treatment stop date is missing, it will be imputed as follows: 
 • If any of EW Visit date, Visit 12 (Week 52/Day 364) date or date of death are non-missing then the study treatment stop date will be imputed as the minimum of (EW Visit date, Visit 12 (Week 52/Day 364) date, date of death, date that all study treatment containers were returned). 
For all other missing treatment stop dates, the last recorded exposure start or stop date will be used.

Study Completion Definition

 • A participant is considered to have completed the study if they have not withdrawn and attended Visit 12.

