3. PLANNED ANALYSES

3.1. Final Analyses

The final planned primary analyses will be performed after the completion of the following sequential steps:

1. All participants have completed the final (early withdrawal) visit, are deemed lost to follow-up or are deceased.
2. All required database cleaning activities have been completed and final database release (DBR) has been declared by Data Management.
3. All criteria for unblinding the randomization codes have been met.
4. Randomization codes have been distributed according to RandAll NG procedures and study is unblinded.
5. Database freeze (DBF) is declared by Data Management.

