10.6.4. Safety

Adverse Events
AEs of Special Interest

 • AESI are defined as events in the 'Infective pneumonia' SMQ in the MedDRA version current at the time of reporting.

Maximum/Minimum Post-Baseline and Worst-Case Post-Baseline	
Definition	Reporting Details
Maximum post-baseline (QTcF, QTcB, PR interval, ECG heart rate, pulse rate, systolic BP, diastolic BP and laboratory tests)	Change from baseline of maximum value over all time-points after Day 1
Minimum post-baseline (Diastolic BP and laboratory tests that do not have a lower limit = 0)	Change from baseline of minimum value over all time-points after Day 1
Worst case post-baseline (ECG findings)	
 • 'Abnormal' if any on-treatment assessment is evaluated as 'Abnormal' • 'Unable to evaluate' if all on-treatment assessments are 'Unable to evaluate' • 'Normal' if any on-treatment assessment is evaluated as 'Normal' and there are no on-treatment assessments evaluated as 'Abnormal'

NOTES:

- The treatment phase definitions specified in Section 10.4.1 will be used and only assessments within the on-treatment period will be considered in assessment of minimum/maximum/worst-case post-baseline.
- Assessment of minimum/maximum/worst-case post-baseline will include on-treatment data from scheduled, unscheduled and study treatment discontinuation visits (if applicable)

Laboratory Parameters
General

 • NQ laboratory results will be treated as missing in summary displays. However, the results will be listed as received (e.g. '<x' or '>x'). • A 'worst case post-baseline' change classification will be derived, in which participants will be counted in the 'to low' and 'to high' categories if they reported a change from an 'in range' baseline to a value below or above the PCI criteria (respectively) at any scheduled or unscheduled on-treatment visit. Participants who did not report a change to a value outside the PCI criteria at any visit after the start of study treatment will be counted in the 'to w/in range or no change' category.
Multiple Measurements for On-Treatment Visits for Safety

Laboratory Parameters
General

 Participants having both high and low values relative to PCI criteria at post-baseline visits for safety parameters will be counted in both the high and low categories of the “worst case post-baseline” row of related summary tables.

ECG
General

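### SAP Section 10.6.1's fallback for a missing treatment stop date can return an exposure start date and so class later safety data as post-treatment

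*SAP*

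**What the plan says.** SAP Section 10.6.1 imputes a missing study treatment stop date in two branches.

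- The first branch applies "If any of EW Visit date, Visit 12 (Week 52/Day 364) date or date of death are non-missing". It takes the earliest of those dates and the date all study treatment containers came back.
- The second branch covers everyone else: "For all other missing treatment stop dates, the last recorded exposure start or stop date will be used". The container-return date plays no part here.

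Section 10.4.1.3 ties the treatment-emergent flag to the result: "If the study treatment stop date is missing, it will be imputed as described in Section 10.6.1", with the window "Study Treatment Start Date ≤ AE Start Date ≤ Study Treatment Stop Date + 3 days". Section 10.4.1 puts the same limit of stop date plus 3 days on assessments. For maximum, minimum and worst-case safety results, Section 10.6.4 states that "only assessments within the on-treatment period will be considered".

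The stop date also sets exposure duration (Section 10.6.2), the last usable rescue-use day (Section 10.6.3) and the concomitant medication phases (Section 10.4.1.1).

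The note closing Section 10.4.1.2 points the other way for events: "assume on-treatment unless there is evidence to the contrary". Section 10.4.1.3 has no such note.

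**The concern.** A stop date may be missing because the last exposure record was never closed. The latest exposure date on file is then that record's start. The fallback so converts evidence that a participant was beginning a period of treatment into the date on which treatment is taken to have ended. A known container-return date cannot correct it.

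Section 2.1 names safety as the primary interest of the revised reporting. An SAE or AESI more than 3 days after the imputed date would be missing from Table 3.7 or Table 3.9. Section 10.10.5 lists no table of post-treatment SAEs to pick it up. Laboratory, ECG and vital sign values in the same span would drop out of the maximum, minimum and worst-case displays.

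**Working it through.** The SAP states no figure for this point, so there is none to reproduce. The check applies its own date rules.

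**Inputs**
- Nominal visit days (Appendix 2): 1, 14, 28, 56, 84, 112, 140, 168, 224, 280, 364.
- On-treatment ends at stop + 3 days (Sections 10.4.1 to 10.4.1.3).
- Exposure duration = stop − start + 1 (Section 10.6.2).
- Last slotted rescue-use day = the earlier of Day 364 and stop − 1 (Section 10.6.3).
- The layout of the exposure records is not given. Two layouts are assumed to show the range.

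**Layout A (assumed): a single record opened on Day 1 and never closed.** The imputed stop is Day 1.
- Exposure = 1 − 1 + 1 = 1 day.
- On-treatment ends on Day 1 + 3 = Day 4, so every visit from nominal Day 14 on is post-treatment.
- No rescue-use day from Day 1 on is slotted.
- With last contact on Day L, L − 4 of L days are post-treatment: 24/28 (85.7%) for Day 28, 80/84 (95.2%) for Day 84, 164/168 (97.6%) for Day 168 and 276/280 (98.6%) for Day 280. Attendance at Visit 12 would supply a date for the first branch, so Day 364 is not a case.

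**Layout B (assumed): a new record opened at each visit, the last one never closed, contact lasting until just before the next visit.** Four days of the last interval stay on-treatment (the start day plus 3).

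| Last interval | Days | Post-treatment days | Share |
|---|---|---|---|
| Day 1–14 | 13 | 13 − 4 = 9 | 69.2% |
| Day 14–28 | 14 | 14 − 4 = 10 | 71.4% |
| Each 4-week interval, Day 28 to 168 | 28 | 28 − 4 = 24 | 85.7% |
| Day 168–224 and 224–280 | 56 | 56 − 4 = 52 | 92.9% |
| Day 280–364 | 84 | 84 − 4 = 80 | 95.2% |

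Under B, the last record starts at about the last attended visit. Scheduled clinic values therefore mostly stay on-treatment. AEs and unscheduled values are the ones reclassified.

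**Examples**
- Layout A, Day 28 laboratory sample: 28 > 1 + 3, so post-treatment. If the stop date were a last attended visit on Day 84, 28 ≤ 84 + 3, so on-treatment.
- Layout B, open record from Day 84, SAE on Day 100: 100 > 84 + 3 = 87, so not treatment-emergent under Section 10.4.1.3. A rule based on the last attended visit would not change this if that visit was also Day 84. Only the default in the Section 10.4.1.2 note would keep the SAE on-treatment.

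**The case against.** The strongest reply is that the rule has narrow reach and a respectable basis.

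- **Reach.** A reader might infer that everyone lost without an early-withdrawal visit is affected. The SAP does not support that. A lost participant with a recorded stop date never enters the imputation, and one whose latest exposure date is a stop date does not receive a start date. Section 3.1 expects that "All participants have completed the final (early withdrawal) visit, are deemed lost to follow-up or are deceased", and those who attend that visit or die have a date for the first branch. The branch can be reached, but the number in it is unknown and could be nil.
- **Outputs.** Nor are the data lost. Among the AE tables, only 3.7 and 3.9 carry an on-treatment label that the imputed date could affect. Tables 3.1 to 3.5 and 3.8 do not, and Listings 15 and 18 to 20 show the events. Section 10.3.1 reports visit data by nominal visit. All reporting is descriptive (Section 2.4).
- **Direction.** A reader might infer that the error always removes on-treatment events. If dosing really ended soon after the last recorded exposure date, there is no material error. That date is also a defensible convention for exposure duration.
- **Conflict.** The Section 10.4.1.2 note is a partial safeguard as much as a contradiction, since it could keep these AEs on-treatment. However, the SAP does not say whether an imputed stop date counts as contrary evidence, and Section 10.4.1.3 has no such default.

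All four points stand as limits. None of them justifies using an exposure start date to cut off safety data when later participation is on record.

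**Conclusion.** The point holds in a limited form. For a participant with a missing stop date, no early-withdrawal, Visit 12 or death date, and an unclosed last exposure record, the rule as written makes a start date the stop date. It can then misclassify on-treatment safety data.

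The size per participant depends on a layout that the SAP does not show. It is 9 to 80 days of the last visit interval with one record per visit, or everything after Day 4 with one record open from Day 1. The second figure is the extreme under an assumption and should not be read as the expected case. At the planned 50 per arm, one such participant is 1/50 = 2% of an arm.

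Separately, Sections 10.4.1.2 and 10.4.1.3 leave open how an AE after an imputed stop date is classified. Two programmers could flag the same event differently. The rule should be corrected, but nothing in the SAP shows that any reported result would change materially.

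**What to change.** Amend Section 10.6.1 for phase classification only:

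1. When the fallback yields an exposure start date and later treatment-period participation is recorded, do not use that date as the stop date. Use the later of the last recorded exposure date and the last attended treatment-period visit, excluding the follow-up visit, capped at the container-return date when known. State whether unscheduled visits count.
2. State in Section 10.4.1.3 that the on-treatment default of Section 10.4.1.2 governs when the stop date is imputed. This covers AEs after the last visit, which step 1 does not reach.
3. Keep the last recorded exposure date for exposure duration if preferred, and say which date drives rescue-use slotting.
4. List every imputed stop date with the branch that produced it.

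Taking the latest of all contact dates would go too far. Follow-up may fall up to 28 days after the last dose, the diary and sensor record rescue medication rather than study treatment, and containers may come back late.

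The cost is a few sentences and minor programming, best done before unblinding. The downside is that some off-treatment days may be counted as on-treatment, which is the cautious direction for safety.
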